**6.0      Recruitment Methods**

Upon IRB approval, the two NHs will be contacted by telephone and email to provide follow-up information about this research study, its objectives and their role in recruitment. (*Please see attached*). A meeting will be scheduled with the request to meet as many of the NH's management team as possible. For these face-to-face meetings informative flyers with background information and simplified research procedures will be provided. (*Please see attached*). In addition, every effort will be made to recognize the NH's contribution to the study including: a plaque for participation, a presentation of the results of the study, and an LSB toolkit donated for continued use with other residents. This toolkit will include: portable scanner, scrapbook albums, audio recorder, USB flash drives and pad and pens.

NH administrators will be asked for the name of a staff member who might serve as an on-site point of contact. This site coordinator would be the research team's point of contact for scheduling, data collection and other communication between the research team, participants and the facility. NH staff have many demands for their time, so this site coordinator will be offered a stipend of \$300.00; \$150.00 halfway through the data collection (or at post-test 1) and \$150.00 when the data collection is complete (or at post-test 2).

Non-probability voluntary sampling method will be used to recruit participants from these two NHs. The NH administration, together with the PI, will identify potential participants. If there is an active resident council at the NH, this group may be contacted in order to introduce the study and recruit potential participants. Every NH, certified by Medicare and Medicaid, must provide a space for councils to meet. Resident councils are a group of residents that meet on a regular basis to discuss concerns, provide suggestions and plan activities for the NH [34].

Additional information meetings will be arranged, as needed, with the assistance of the NH administration, to describe the study and to answer residents', staff, and any family members' questions. (*Please see attached information flyer*).

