### **3.0 Inclusion and Exclusion Criteria**

Two Medicare and Medicaid certified NHs, located in Harris and Fort Bend Counties, and freestanding, or ones that are not a part of a hospital or a continuing care retirement community, will be invited to participate in this research.

Residents of the two selected NHs, ages 57 and older and who have the ability to speak English, will be invited to complete an eligibility screening to participate in this study. Eligibility will be determined using the Six-Item Screener (SIS), as measured by a score of 4 or higher for cognitive impairment.

**The Six Item Screener (SIS)** was specifically developed from the Mini-Mental State Examination (MMSE) to screen subjects for cognitive ability to participate in research studies. The SIS was found to have good test-retest reliability (.705), internal consistency (.82) and sensitivity (.90) [29]. The scale is unobtrusive, only takes 1-2 minutes to complete and can easily be incorporated into the initial eligibility assessments [30]. (*Please see attached screener*).

Exclusion criteria will consist of residents who scored less than 4 on the SIS, indicating cognitive impairment; individuals who do not speak English; and individuals who are not residents of the participating NH.

**FULL PROTOCOL TITLE:** The Effectiveness of Life Story Book on Depression and Meaning in Life for Mentally Alert Residents of Nursing Homes

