## **4.0 Vulnerable Populations**

Mentally alert residents of the two NHs are eligible to participate in this study with safeguards included to protect the welfare, safety, privacy and confidentiality of this vulnerable population.

The NH administration will assist in identifying potential participants, but the research team will assure the residents that participation is completely voluntary, and that refusal to participate will not compromise their relationship with the staff or their care.

Due to institutionalization residents are more susceptible to coercion. There is the potential that residents may feel that they cannot refuse participation when asked by staff, due to the fact that residents depend upon that staff for food shelter, health and social services [31]. Again, assurances by the research team will be made that participation is completely voluntary and that they may decline participation.

Using the SIS for screening eligible also ensures that the participants have the cognitive ability to understand what will happen in the research, what risks may be involved, and that participation is voluntary. In addition, the research team will conduct all eligibility screening in private and the results of the SIS will be kept confidential and will not be shared with the potential participant or the NH staff. Potential participants who do not meet the inclusion criteria will be informed that for this study they are not eligible. No identifying information will be collected from them.

All scoring of instruments administered will be kept confidential and will not be shared with the NH staff.

Residents may have hearing or vision problems and may therefore require more time to have the study explained to them. Information flyers and informed consents will be read to the residents, along with using larger font.

Although this population is vulnerable, this research proposes minimal risk and will directly benefit participants in providing them with a life story book of their own and has the potential to reduce depressive symptoms and increase MIL.

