[name] is an Assistant Professor at the University of Houston College of Nursing and named a 2018 Salute to Nurses Top 15 winner. She has served as an oncology nurse for 37 years and is certified in gerontology. In addition, [name] is a certified instructor for Reminiscence and Life Story Work. She will serve as a consultant on this study.

The two NHs that will be recruited will be described upon their consent and letters of cooperation will be obtained. The NHs will be comparable on the following five aspects: number of long-stay residents, overall quality rating, staff rating, type of ownership (private, public or government) and facility size. Each of the NHs participating in this study will have a minimum of 85 residents. According to the Vital Statistics report- *Long-Term Care Services in the United States: 2013 Overview*, there are about 49.6% of NH residents who are mentally alert [3]. With approximately 50% of NH residents being mentally alert, there will be approximately 42 residents to recruit from the NHs that house 85 residents.

Two social work/medical professionals will be hired as research assistants. Once they are hired, I will submit an IRB modification with their information.

An IRB modification with the two site coordinators information, along with the nursing home letters of cooperation, will be added.

Recruitment will begin immediately upon IRB approval and will continue until the minimum of 10 and maximum of 12 participants from each NH (Total 20 minimum and 24 maximum) are recruited. Transcription will begin immediately after each LSB visit with participants and data will be analyzed after all data collection is complete. We anticipate that we will be able to complete the intervention three months following IRB approval. The LSB intervention and analyses should be completed within six months following IRB approval.

**FULL PROTOCOL TITLE:** The Effectiveness of Life Story Book on Depression and Meaning in Life for Mentally Alert Residents of Nursing Homes

Adequate psychological and/or medical resources are available and can be provided by the NHs for those who may need it as a result of an unanticipated consequence of research participation.

The research team will communicate on an ongoing weekly basis to discuss any issues that may arise so as to ensure successful execution of this research study. All of the key personnel listed in this study have read and understand this protocol.

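### Residents enter the trial by identification in each home with no common rule and an optional council route, so any difference in selection is confounded with condition up to post-test 1

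*Combined protocol and SAP*

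**What the plan says.** Four sections bear on how a resident reaches screening.

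- **3.0 Inclusion and Exclusion Criteria** describes an invitation by age and language: "Residents of the two selected NHs, ages 57 and older and who have the ability to speak English, will be invited" to screening with the Six-Item Screener (SIS).
- **4.0 Vulnerable Populations** gives the home a supporting role: "The NH administration will assist in identifying potential participants".
- **6.0 Recruitment Methods** declares the approach, "Non-probability voluntary sampling method will be used to recruit participants from these two NHs", and then gives the home and the PI the task jointly: "The NH administration, together with the PI, will identify potential participants". It adds a conditional route: "If there is an active resident council at the NH, this group may be contacted", both to introduce the study and to recruit. Further information meetings are held as needed.
- **10.0 Procedures Involved** has the PI administer the SIS at private meetings held once candidates have been identified.

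On design, 10.0 allocates two homes at random, one to each sequence, and everyone in a home receives the same condition. On numbers, 5.0 recruits 10 to 12 residents per home, and 29.0 Resources expects that "there will be approximately 42 residents to recruit from the NHs that house 85 residents".

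Three safeguards are stated. The homes are to be comparable on five facility-level aspects (29.0). Demographic variables are compared at baseline, and pre-test scores are covariates in the MANCOVA (both 25.0).

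**The concern.** Identification decides who can be screened, and the text does not say how it is done. Two administrations could in good faith apply different ideas of a suitable candidate. A council might supply participants in one home and not in the other. In a trial that randomised individuals, this would affect mainly generalisability. Here home and condition are the same thing until post-test 1, so it affects the comparison itself.

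What is at stake is the between-group contrast on the depression scale (GDS-12R) and the Meaning in Life Questionnaire (MLQ). Traits such as sociability, family contact and readiness to reminisce could plausibly affect the response to an intervention built on storytelling and photographs. None of them is measured. If they differ between homes because of how residents were found, an LSB effect could be created or hidden. NH-B's later LSB phase gives a second implementation but does not repair the contrast at post-test 1.

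**Working it through.** **1. The sections side by side.** Section 3.0 gives criteria for those invited but does not say that every resident who meets them will be approached. Section 4.0 says the administration assists, 6.0 says it identifies candidates with the PI, and 10.0 puts screening after that. The four can be read together: candidates are identified, met privately, then screened. They leave open how candidates are found and whether it is done alike in both homes. Section 10.0 also does not say whether homes are allocated before candidates are identified. If they are, identification could be made knowing the condition.

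**2. Room for selection.** Inputs are 85 residents as the minimum home size and 49.6% mentally alert (both 29.0), and 10 to 12 places per home (5.0).

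- Pool: 85 × 0.496 = 42.2, which reproduces the plan's figure of about 42.
- Share enrolled: 12 / 42.16 = 28%; 10 / 42.16 = 24%.

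For a home of that size the pool is an upper bound, because age, language and willingness have not been applied to it. The figures show that selection is possible. They do not measure bias.

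**3. What the safeguards reach.**

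- The five aspects in 29.0 describe facilities, not the residents who enter.
- The covariates in 25.0 adjust for pre-test GDS-12R and MLQ, not for the traits named above.
- The baseline comparison covers the demographics listed in 10.0. Marital status, education and length of residence are partial proxies at best. The comparison is also weak at this size. For a two-sided .05 t-test with n per home and a true imbalance of b SD, the noncentrality is b × √(n/2) on 2n − 2 degrees of freedom. With b = 0.5, the probability of detection is 18.5% for n = 10 and 21.6% for n = 12.

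**4. Illustration of consequence (assumed inputs).** Suppose LSB does nothing and selection alone leaves an outcome difference of b SD between homes. The same formula, for a simple t-test on one outcome standing in for the MANCOVA, gives these false-positive rates:

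| b (assumed) | 10 per home | 12 per home |
|---|---|---|
| 0.10 | 5.5% | 5.6% |
| 0.25 | 8.3% | 9.0% |
| 0.50 | 18.5% | 21.6% |

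Pre-test adjustment would lower these by an amount the documents do not allow to be estimated.

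**5. Workload of a common list.** Assume the 49.6% applies to listed residents and that the SIS separates them accordingly.

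- No refusals: 12 / 0.496 = 24.2, about 24 screenings per home.
- Half decline (assumption): 12 / (0.496 × 0.5) = 48.4, about 48 approaches.
- Only 30% agree (assumption): 12 / (0.496 × 0.3) = 80.6, about 81 approaches, which is tight in a home of 85.

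**The case against.** Much can be said for the plan. It openly declares a non-probability, voluntary sample and a quasi-experimental design. The PI shares in identification in both homes and administers every SIS, which gives some common handling. Section 6.0 also points to an attachment on the homes' role in recruitment. It is not in the file, so the absence of a rule can be asserted only for the text available. Nothing in the documents shows that either administration would favour a particular kind of resident, or that council members differ from others.

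These points limit the claim but do not remove it. Declaring a method does not make it the same in both homes, and one shared person is not a written rule.

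Three stronger readings are tempting and not supported:

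- *That 3.0 and 6.0 contradict each other.* Section 3.0 never says that all qualifying residents will be invited, and to identify potential participants is not to hand-pick them.
- *That about 71% of the pool (30 of 42) is passed over by staff judgement.* With 12 places for 42 residents, that share goes unenrolled under any method, including random order, and some of those residents would be ineligible or decline.
- *That staff will pressure residents.* Section 4.0 does acknowledge that "There is the potential that residents may feel that they cannot refuse participation when asked by staff", but it answers this with assurances from the research team and private screening. No section says that staff enrol residents.

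A last objection also stands: random order of approach does not make two homes' populations alike, nor equalise who volunteers.

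**Conclusion.** The concern holds in limited form. The plan leaves entry to identification within each home, with a council route that may operate in only one of them, and home coincides with condition up to post-test 1. Any difference in identification is therefore confounded with LSB versus care as usual, and the stated safeguards address it only in part.

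Its size and direction cannot be estimated. A reader might assume a 0.5 SD difference in an unmeasured trait and a partial correlation of .3 to .5 with outcome, giving 0.5 × .3 to 0.5 × .5 = 0.15 to 0.25 SD. That is only the product of assumed inputs, and the documents supply neither. The false-positive rates in the illustration are conditional in the same way.

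The conclusion rests on the design (one home per condition) and on the available text containing no common procedure. It would weaken if the recruitment attachment set one. A common procedure is a cheap improvement that the trial should adopt.

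**What to change.** In 6.0, replace the identification sentence and the council provision with one procedure for both homes:

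1. The site coordinator lists residents who meet the age and language criteria of 3.0, by room or list number only.
2. The research team puts each list in random order and approaches residents in that order for SIS screening until 12 are enrolled in the home.
3. The resident council is used only to announce the study, in the same way in both homes.
4. Anonymous counts are kept per home: approached, declined, SIS below 4, enrolled.

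Align 3.0 and 4.0 with this. Participation stays voluntary, and the home no longer chooses whom to approach, which suits the concern in 4.0 about residents' freedom to refuse.

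**Cost.** No new staff, but more approaches and more 10-minute screenings, as worked out above. The list must be handled within the plan's privacy provisions, including the undertaking in 4.0 to collect no identifying information from residents found ineligible.

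**What remains.** This removes differential selection by staff or council. It does not remove differences between the two homes' populations or in who volunteers, so the report should still state the confounding of home with condition as a limitation. If the list proves impractical, the counts alone would still let readers compare entry between homes.

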**7.0      Multi-Site Research Communication**

N/A

**8.0      Study Timelines**

- (1) Eligibility screening – 10 minutes
- (1) Initial visit, consents, study overview and instruments   60-90 minutes
- (5) Intervention visits – 60-90 minutes
- (1) Potential visit for NH-B if any edits were required to their LSB   30-60 minutes

Total maximum time for participation after screening = 10 hours

**FULL PROTOCOL TITLE:** The Effectiveness of Life Story Book on Depression and Meaning in Life for Mentally Alert Residents of Nursing Homes

Immediately upon IRB approval, recruitment will begin and will continue until a minimum of 10 and a maximum of 12 from each NH are recruited (Total for both NHs- 20 minimum and 24 maximum). The intervention will begin as soon as recruitment levels are met. Transcription will begin after the first LSB visit and will continue until all LSBs are complete. The intervention will take 10 weeks to complete. At the conclusion of all data collection and transcription activities, data analyses will be conducted. We anticipate that that we will be able to conduct the intervention within four months following IRB approval. Primary analyses should be completed within six months following IRB approval. (*See attached timeline*).

## **9.0 Study Endpoints**

This is a minimal risk study. There are no safety endpoints given, because there are no safety risks associated with the study.

## **10.0 Procedures Involved**

### *Study Design:*

A quasi-experimental switching replication design will be employed to examine the effects of LSB on depressive symptoms and MIL for residents of NHs who are mentally alert by comparing post-test scores, while controlling for pretest scores. Two comparable NHs will be randomly allocated to NH-A or NH-B, indicating which home will begin LSB first, whereas the other home will receive care as usual. Participants in the same NH will receive the same intervention. A summary of the design is as follows:

Nursing Home A (NH-A):	Pretest	LSB	Post-test	CAU	Post-test
Nursing Home B (NH-B):	Pretest	CAU	Post-test	LSB	Post-test (CAU = care as usual)

Both NHs will eventually receive the LSB intervention, which will provide another opportunity to test outcome measures and allow for two independent implementations of the LSB intervention. This is one of the more ethically feasible designs because all participants will eventually receive the intervention. Furthermore, the additional post-test for NH-A, after one month, will examine the lasting effects of the LSB intervention.

### *Description of all research procedures being performed and when they are performed:*

After identifying potential participants, private informational meetings with the research team which will include the PI and two research assistants -will be conducted with each potential participant where initial screening, using the SIS, will be administered by the PI. (*Please see attached screening script/tool*). If the resident is eligible, and would like to participate, the research team will further explain the study, including the length of the study-10 weeks with six visits, length of the visits 1- hour, three weeks with no visits, and the measures that will be

**FULL PROTOCOL TITLE:** The Effectiveness of Life Story Book on Depression and Meaning in Life for Mentally Alert Residents of Nursing Homes

collected. Full disclosure and written consents will be explained with plenty of time for any questions or clarification before consent forms are signed. The consent form will include the purpose, procedures, risks and costs of participating in the LSB. Again, there will be no costs for participating in the study and the research team will receive no monetary income from the LSB. In addition, the LSB will be the property of the participant, along with any scanned photos or stories written. This will be signed by each participant, each RA, and the PI. A copy of the consent form will be given to each participant. Additional information will be provided for those participants who would like to request their family's cooperation to secure photos and/or memorabilia. (*See attached information sheet*).

Although the recruitment of participants is for mentally alert residents, if they have given durable power of attorney to others, it may be necessary, per their NH regulations, to obtain informed consent from their designated durable powers of attorney [35], [36], [37]. The durable power of attorney will be contacted, permission sought, and the consent form signed. The consent form will also include an agreement that the LSB ownership will be with the participant. [38] A copy of the consent form will be given to the durable power of attorney.

Participants will be notified for scheduling of the LSB intervention, by their preferred method of notification, once recruitment is completed. When participant recruitment levels are met, the research team will contact the participants to schedule their first visit. LSB visits for all participants will begin the same week.

Potential participants who do not meet the inclusion criteria will be informed that for this study they are not eligible. No identifying information will be collected. They will also be informed that a presentation of the study results will be presented at their NH at a later date, to which they are invited to come and hear the results.

Two RAs will be randomly assigned six participants from each of the two NHs. Each will conduct individual LSB sessions with these six participants per NH, or twelve from both homes.

For the first visit, all 24 participants will be individually visited by the PI and the RA assigned to those participants. Each RA will only visit those participants whom they will be providing the intervention. An overview of the study will be reviewed, as well as information regarding the number of visits and length of time for each visit (1 hour). This first visit will also be a time for the participants to get acquainted with their RA. Participants will review the consent form signed in the initial screening interview which will include the purpose, procedures, risks and costs of participating in the LSB, as well as the protection of confidentiality from the RA and the PI. They will also be reminded of their rights as participants. The participants, at the beginning of each visit, will be told that they can stop and rest at any time or may reschedule the session if they become too fatigued to continue.

The PI will administer all measures face-to-face on a tablet, which will include the MLQ and the GDS-12R. In addition, the PI will collect orally from the participants their demographic information and their functional status (Katz ADL) onto a tablet.

**FULL PROTOCOL TITLE:** The Effectiveness of Life Story Book on Depression and Meaning in Life for Mentally Alert Residents of Nursing Homes

At this first visit, a written reminder card will be given to each participant with the date, time and contact information of their RA and their next scheduled visit. (*Please see attached*). Scheduled visits will be done at the most convenient time for the participant with careful consideration of scheduled activities, i.e. meals, naps, medicine. All future visits will be scheduled at this time, with the understanding that the RA will be flexible to the needs of the participant.

NH-B participants will be scheduled for post-tests in 4 weeks, which will include repeating an overview of the study, including the number of sessions and length of time for each session. A written postcard will be given to each participant with the date, time and contact information of their RA for their scheduled post-test. A follow-up postcard will be sent to the participant each week until week # 4, when a reminder phone call will also be made by their RA the day before their visit is scheduled. Until that time, the resident will continue to receive care as usual in their NH.

*Description of the Intervention:*

**Life Story Book.** LSB provides a person the opportunity to chronologically share their life experiences and memories [25]. The LSB will include a combination of written information, photographs of significant people, places or events, and personal narratives from the stages of life that the participant would like to include.

The duration of the intervention will be three-1-hour visits, not including the visits for the pretest and the post-tests measures collected, for a total of five visits. Each visit will begin with the RA assessing the environment and the participant's needs, making sure that the participant can hear and see the RA, and that the seating arrangement is comfortable before beginning. Assessing the environment will include: assessing for privacy, lighting, noise level, temperature and seating arrangement [39]. It will be important to monitor the participant's needs for any other difficulties assessed that may need to be tended to and adjustments or accommodations made. This is crucial to adequately accommodate the older adults' needs. Again, the RAs will remain flexible in regard to the length of time per visit for the sake of the older participants. For example, two 30-minute sessions may be used, as could rescheduling for health issues, or other creative ways to accommodate the needs of the participant as much as possible.

Each resident will be guided by their RA through memories of their life using extracted questions from the Life Review and Experiencing Form (LRF) created by Haight & Haight and based on Erik Erikson's life stages model [39]. (*Please see attachment*). The purpose of using these questions from the LRF is to achieve some structure for gathering memories across the life span; beginning with childhood and adolescence, moving onto family, home and finally adulthood and a summary of the life review [39]. Reviewing life from childhood until the present enables the participant the opportunity to think about recalled and reconstructed memories, related facts and significant experiences [39]. Birren & Cochran suggest [21] reminding the older adult of their five senses-touch, sight, taste, hearing and smell- for obtaining details of a story; for example, at a holiday event was their food? Dancing? Singing? While the RA will have the list of questions to guide the participant through life stages, they will use the questions as prompts or suggestions. The RA will listen closely and respond to the participant while encouraging the participant to

**FULL PROTOCOL TITLE:** The Effectiveness of Life Story Book on Depression and Meaning in Life for Mentally Alert Residents of Nursing Homes

lead the dialogue and continue talking and recalling [21], [39]. Participants will be free to decline to answer any questions.

The RA will act as a scribe but will also use an audio recorder. The use of an audio recorder will free the RA up to listen attentively and respond appropriately to their participant's stories. Audio recording will also aid the RA in accurately writing their participant's stories. A professional transcriber will be hired to assist, as needed, for transcription of stories.

Any pictures and/or memorabilia chosen by the participant will be scanned at the NH using a portable scanner. This will ensure that no photos and/or memorabilia are removed from the participants' NH. The research team will print (using a portable printer) and insert these photos into the participant's LSB. The RA may help the participant to create a short caption, in the participant's own words, to be placed under each photo. Again, the resident's family may be contacted, with the approval of the resident, to assist with the collection of newspaper clippings, photographs, and/or other memorabilia. Substitute photos of relevant places may be located on the internet by the RA as requested or needed. For example, a picture of their high school located and printed for their book.

After post-test measures are administered, when the LSB is completed, both the participant and their RA will review the book, obtain clarification and/or corrections and remove anything the participant would rather not have in their book, and finalize the details of the book. The participant will own their own LSB and will have the final say of what is, or is not, included [19], [40]. To ensure that the LSB can be added to and updated, an expandable scrapbook album will be used with additional blank pages added. This also reflects that a person's life story is never finished [41]. If there are corrections to be made, the book will be corrected and returned to the participant as soon as possible.

All audio files will be destroyed immediately after transcription.

A presentation of results will be scheduled where each nursing home will receive a plaque and life story kit for participating in this research. The presentation will include the components of videotaping and/or photographs. A supplemental informed consent form indicating preference to be video recorded and/or photographed at the presentation of results, including a UH Media piece, will be obtained by those participants willing to be identified as participants. Every effort will be made to ensure that participants know this is completely optional and would nullify their previous research consent form signed, in which it was stated that they would not be identified as participants

*What data will be collected, including long-term follow-up?*

At the first visit the PI will administer the following instruments in face-to-face interviews with each screened participant. Residents' characteristics measures will include socio-demographic data and a functional status survey. The socio-demographic data that will be collected for each participant will include: year born, gender, marital status, level of education, ethnicity, religion, and length of residence in the NH. (*Please see attached instruments*).

**FULL PROTOCOL TITLE:** The Effectiveness of Life Story Book on Depression and Meaning in Life for Mentally Alert Residents of Nursing Homes

**Katz Index of Independence in Activities of Daily Living** (ADLs) will be administered in order to assess the functional status of the participant's ability to perform activities of daily living independently. This tool is one of the most commonly used tool to measure an older adult's functional status. The Index ranks the adequacy of performance in six areas of function: bathing, dressing, toileting, transferring, continence, and feeding. Persons are scored yes/no for independence in each of the six functions. A score of 6 indicates full function, 4 indicates moderate impairment, and 2 or less indicates severe functional impairment. The instrument is used effectively among older adults in the community and all care settings. This is a scale of the six activities of daily living [42].

**Geriatric Depression Scale (Residential) (GDS-12R)** is a shortened version of the 30item Geriatric Depression Scale which has been shown to effectively distinguish depressed from non-depressed older adults [43]. In 1986, a short form of 15-items (GDS-15) was developed for older adults, from the original 30-item questionnaire, primarily for brevity and for use with older adults with health issues or those with dementia. It was found to have a high correlation with depressive symptoms in previous validation studies [44]. Three items were found to not be reflective of residents of nursing homes and these three were omitted from the GDS-15 to create the GDS-12R, which increased the alpha from .76 to .81 [45]. The GDS-12R was found to have good internal consistency and test-retest reliability [45]. It is a self-report scale of depressive symptoms and uses a yes/no format. The scale measures how the person has felt during the previous week and usually takes 5 to 7 minutes to complete, making it ideal for older adults in residential facilities. Scores  $\geq 5$  are significant for depressive symptoms [46].

**Meaning in Life Questionnaire (MLQ)** will be used to measure MIL. Steger et al. MLQ [47] has two subscales which assess the presence of meaning (how much a person feels their life has meaning) and the search for meaning (how much a person strives to find meaning and understanding in their life) [48]. The two-subscale measure consists of 10 items on a 7-point Likert scale, ranging from 1-absolutely true to 7-absolutely untrue: five items for presence of meaning and five items for search for meaning. This questionnaire has been shown to have high convergent and discriminant validity and has been tested across age, gender, race, and national groups [47], [48]. The MLQ questionnaire does not have cut off scores like the Geriatric Depression Scale, but based on numerous studies, a score  $> 24$  indicates a person feels their life has meaning and purpose [48].

The GDS-12R and MLQ will be administered by the PI at three times; pre-test, post-test 1, and post-test 2. These measures will be administered orally to each participant and answers recorded by the PI on a tablet.

One open-ended feedback, qualitative, question will be asked of participants at post-test 2: "What did you think of the experience of participating in Life Story Book?" This question will be documented in writing with no names or ID numbers recorded.

*(See attached intervention table/timeline).*

**FULL PROTOCOL TITLE:** The Effectiveness of Life Story Book on Depression and Meaning in Life for Mentally Alert Residents of Nursing Homes

